7.1.4. Final analysis

The **final** analysis will evaluate all data pertaining to primary and secondary safety and immunogenicity endpoints. It will be performed by the GSK Biologicals biostatistics team when all primary and secondary endpoint data up to study end (last Visit 5-NB) are available.

Results will be presented in a clinical study report. This report will include results summarized by study group as well as individual (by subject) data /data listings, and will be made available to investigators.

CONFIDENTIAL209544 (RSV MAT-004)
Statistical Analysis Plan Amendment 3

If the data for tertiary endpoints become available at a later stage, (an) additional analysis/ analyses will be performed. These analyses will be documented in annex(es) to the clinical study report.

Description	Disclosure Purpose (CTRS=public posting, SR=study report, internal)
Final Analysis (E1_01)	Public disclosure, Study report
First Analysis (E1_02)	Internal
Second Analysis (E1_03)	Internal
Third Analysis (E1_04)	Internal

7.2. Statistical considerations for interim analyses

The first 3 analyses will be descriptive. Therefore, the conduct of these analyses has no impact on interpretation of study results.

8. CHANGES FROM PLANNED ANALYSES

To take a more practical approach, subgroup analysis of safety by age category at vaccination (18 - <35; \geq 35 years) in maternal subjects will include summaries of pregnancy outcomes, pregnancy related AESIs, SAEs, MAEs and MA-RTIs.

Subgroup analysis of safety by gestational age at birth (> 37 weeks or \leq 37 weeks) in infant subjects will include summaries of neonatal AESIs, MAEs, SAEs, and occurrence of RSV-associated RTIs, LRTIs, severe LRTIs, very severe LRTIs and RSV-associated hospitalizations.

Subgroup analysis on other safety summaries will be performed if deemed necessary.

Subgroup analysis of immunogenicity by age category at vaccination (18 - <35; \geq 35 years) for maternal subjects and by gestational age at birth ((> 37 weeks or \leq 37 weeks) for infants will include analysis of GMT(C) and GMR calculation at each time point and geometric mean of placental transfer.

Subgroup analysis on other immunogenicity analysis will be performed if deemed necessary.

9. NON-STANDARD DATA DERIVATION RULES AND STATISTICAL METHODS

The following sections describe additional derivation rules and statistical methods which are not presented in section [10.1](#).

CONFIDENTIAL209544 (RSV MAT-004)
Statistical Analysis Plan Amendment 3**9.1. Data derivation****9.1.1. Gestational age at vaccination**

Gestational age at vaccination in weeks for maternal subjects will be calculated based on estimated date of delivery and date of vaccination.

9.1.2. Immunogenicity

For a given subject and given immunogenicity measurement, missing or non-evaluable measurements will not be replaced. Therefore, an analysis will exclude subjects with missing or non-evaluable measurements.

- For the within-group assessment, the descriptive analysis performed for each assay at each timepoint will exclude subjects with a missing or non-evaluable measurement.
- For the between group assessments, statistical model will be fitted based on the subjects having a result at both the baseline and the considered timepoint.

The GMT/GMC and its 95% CI will be obtained by exponentiating the mean and its 95% CI of the log-transformed titres/concentrations. All CI computed will be two-sided 95% CI.

Placental transfer is defined as the ratio of RSVPreF3 IgG-specific antibody concentrations between cord blood (or blood sample from infants collected within 3 days after birth if cord blood is not available) and maternal blood sample at delivery (or within 3 days after delivery if blood sample is not collected during delivery).

9.1.2.1. Assay cut-offs for serology results

A seronegative subject is a subject whose antibody titre is below the cut-off value of the assay. A seropositive subject is a subject whose antibody titre is greater than or equal to the cut-off value of the assay. The cut-off tests for immunogenicity evaluation will be as per following:

System	Component	Method	Unit	Cut-off (LLOQ)	ULOQ
Serum	RSV-A Neutralising Antibody	NEUTRALISATION	ED60	18	123535
Serum	RSV-A Neutralising Antibody	NEUTRALISATION	IU/mL	56	217400
Serum	RSVPreF3 IgG antibody concentrations	ELISA	EU/mL	25	251 769
Serum	RSV-B Neutralising Antibody	NEUTRALISATION	ED60	30	138336
Serum	RSV-B Neutralising Antibody	NEUTRALISATION	IU/mL	44	171279

Note: the assay cut-off (LLOQ), ULOQ and units may be further adjusted at time of analysis, which would not lead to SAP amendment.

9.1.3. RTI and LRTI

Cases will be classified (during data analyses) according to the definitions that follow.

CONFIDENTIAL209544 (RSV MAT-004)
Statistical Analysis Plan Amendment 3**Table 9 MA-RTI case definitions for data analysis in maternal subjects**

RSV-MA-RTI	Medically attended visit for RTI symptoms AND Confirmed RSV infection ^{1,2}
RSV hospitalization	Confirmed RSV infection AND Hospitalized for acute medical condition ³
All-cause MA- RTI	Medically attended visit for RTI symptoms

¹ Confirmed RSV infection defined in Section 4.2.6.3 of the Protocol² RSV (nasal swab) sampling and testing as specified in Table 11 of the Protocol.³ Hospitalization is defined as admission for observation or treatment based on the judgement of a health care provider.**MA-RTI** = Maternal, medically attended respiratory tract illness**Table 10 RTI/LRTI case definitions for data analysis in infants**

RSV-RTI	Runny nose, OR Blocked nose, OR Cough AND Confirmed RSV infection ⁴
RSV-LRTI	History of cough OR difficulty in breathing ¹ AND SpO ₂ < 95% ² , OR RR increase ³ AND Confirmed RSV infection ⁴
RSV-severe LRTI	Meeting the case definition of RSV-LRTI AND SpO ₂ < 93% ² , OR lower chest wall in-drawing
RSV-very severe LRTI	Meeting the case definition of RSV-LRTI AND SpO ₂ < 90% ² , OR inability to feed OR failure to respond / unconscious
RSV hospitalization	Confirmed RSV infection ⁵ AND Hospitalized for acute medical condition ⁶
All-cause RTI	Runny nose, OR Blocked nose, OR Cough
All-cause LRTI	History of cough OR difficulty in breathing ¹ AND SpO ₂ < 95% ² , OR RR increase ³

Definitions based on [Modjarrad, 2016]

RTI = respiratory tract illness; **LRTI** = lower respiratory tract illness; **RR** = respiratory rate; **SpO₂** = blood oxygen saturation by pulse oximetry.¹ Based on history reported by parents/LARs and includes difficulty in breathing (e.g. showing signs of wheezing or stridor, tachypnoea, flaring [of nostrils], chest in-drawing, apnea).² For blood oxygen saturation (SpO₂), the lowest value monitored will be used. In high altitudes (>2500m), SpO₂ <92% for LRTI, <90% for severe LRTI, <87% for very severe LRTI.³ RR increase defined as:

- > 60/minute (< 2 months of age)
- > 50/minute (2 to < 12 months of age)
- > 40/minute (12 to 24 months of age)

⁴ Confirmed RSV infection defined in Section 4.2.6.3 of the Protocol⁵ RSV (nasal swab) sampling and testing as specified in Table 12 of the Protocol⁶ Hospitalization is defined as admission for observation or treatment based on the judgement of a health care provider.

CONFIDENTIAL209544 (RSV MAT-004)
Statistical Analysis Plan Amendment 3

For the analysis of RTI episode, a new RTI episode will be defined as any occurrence of cough, runny nose, blocked nose, wheezing or difficulty breathing with an interval of at least 7 symptom free days since the last episode of RTI that was diagnosed.

9.1.4. Hematology and Biochemistry parameters

The table below shows the toxicity grading during the second and third trimester of pregnancy based on [Sheffield, 2013]

Table 11 Laboratory values during the second and third trimester of pregnancy

Serum chemistries	Normal range for 2nd trimester or uncomplicated pregnancy		Grade 1	Grade 2	Grade 3	Grade 4
Creatinine	0.4-0.8 mg/dL		0.9-1.2	1.3-1.6	1.7-2.5	>2.5 or requires dialysis
BUN	3.0-13.0 mg/dL		14.0-19.0	20.0-30.0	>30	Required dialysis
Haematology	Normal range for 2 nd trimester or uncomplicated pregnancy		Grade 1	Grade 2	Grade 3	Grade 4
Haemoglobin	9.7-14.8 g/dL		9.0-9.6	8.0-8.9	7.0-7.9 or requires a transfusion	<7.0 or li-threatening acute blood loss
Change from baseline value – gm/dL			1.6-2.0	2.1-4.5	4.6-5.0	>5.0
WBC	5.6-14.8 x 1000cell/mm ³	High	>14.8-16.0	>16.0-20.0	>20.0-25.0	>25.0 Signs of septic shock
		Low	<5.5-3.5	<3.5-1.4	<1.4-1.0	<1.0 Signs of septic shock
Lymphocytes	0.9-3.9 x 1000cell/mm ³	High	>3.9-5.0	>5.0		
		Low	<0.9-0.75	<0.75-0.5	<0.5-0.25	<0.25
Neutrophils Absolute neutrophil count	3.8-12.3 x 1000cell/mm ³		<3.8-2.0	<2.0-1.0	<1.0-0.5	<0.5
Eosinophils	0-0.6 x 1000cell/mm ³		>0.6-1.5	>1.5-5.0	>5.0	Hypereosinophilic syndrome
Monocytes	0.1-1.1 x 1000cell/mm ³		≤10% outside of normal rage	>10% outside of normal rage: clinical correlation may be necessary and grading according to it		
Basophils	0-0.1 x 1000cell/mm ³		≤10% outside of normal rage	>10% outside of normal rage: clinical correlation may be necessary and grading according to it		
Platelets	155-409 x 1000 L ⁻¹	Low	125-154	100-124	25-99	<25
		High	410-499	500-749	750-1000	>1000
Liver Function Tests	Normal range for 2 nd trimester or uncomplicated pregnancy		Grade 1	Grade 2	Grade 3	Grade 4
AST (SGOT) Aspartate transaminase	3-33 U/L		>1.0-1.2xULN	>1.2-3.0xULN	>3.0-8.0xULN	>8.0xULN cirrhosis transplant candidate
ALT (SGPT) Alanine transaminase	2-33 U/L		>1.0-1.2xULN	>1.2-3.0xULN	>3.0-8.0xULN	>8.0xULN cirrhosis transplant candidate

CONFIDENTIAL209544 (RSV MAT-004)
Statistical Analysis Plan Amendment 3

Serum chemistries	Normal range for 3rd trimester or uncomplicated pregnancy		Grade 1	Grade 2	Grade 3	Grade 4
Creatinine	0.4-0.9 mg/dL		1.0-1.2	1.3-1.6	1.7-2.5	>2.5 or required dialysis
BUN	3.0-11.0 mg/dL		12.0-19.0	20.0-30.0	>30	Required dialysis
Liver Function Tests	Normal range for 3rd trimester or uncomplicated pregnancy		Grade 1	Grade 2	Grade 3	Grade 4
AST (SGOT) Aspartate transaminase	4-32 U/L		>1.0-1.2xULN	>1.2-3.0xULN	>3.0-8.0xULN	>8.0xULN cirrhosis transplant candidate
ALT (SGPT) Alanine transaminase	2-25 U/L		>1.0-1.2xULN	>1.2-3.0xULN	>3.0-8.0xULN	>8.0xULN cirrhosis transplant candidate
Haematology	Normal range for 3rd trimester or uncomplicated pregnancy		Grade 1	Grade 2	Grade 3	Grade 4
Haemoglobin Change from baseline value – g/dL	9.5-15.0 g/dL		9.0-9.4	8.0-8.9	7.0-7.9 or requires a transfusion	<7.0 or li-threatening acute blood loss
			1.6-2.0	2.1-4.5	4.6-5.0	>5.0
WBC	5.9-16.9 x 1000cell/mm ³	High	>16.9-18.0	>18.0-20.0	>20.0-25.0	>25.0 Signs of septic shock
		Low	<5.9-3.5	<3.5-1.4	<1.4-1.0	<1.0 Signs of septic shock
Lymphocytes	1.0-3.6 x 1000cell/mm ³	High	>3.6-5.0	>5.0		
		Low	<1.0-0.75	<0.75-0.5	<0.5-0.25	<0.25
Neutrophils Absolute neutrophil count	3.9-13.1 x 1000cell/mm ³		<3.9-2.0	<2.0-1.0	<1.0-0.5	<0.5
Eosinophils	0-0.6 x 1000cell/mm ³		>0.6-1.5	>1.5-5.0	>5.0	Hypereosinophilic syndrome
Monocytes	0.1-1.4 x 1000cell/mm ³		≤10% outside of normal rage	>10% outside of normal rage: clinical correlation may be necessary and grading according to it		
Basophils	0-0.1 x 1000cell/mm ³		≤10% outside of normal rage	>10% outside of normal rage: clinical correlation may be necessary and grading according to it		
Platelets	146-429 x 1000 L ⁻¹	Low	125-146	100-124	25-99	<25
		High	430-499	500-749	750-1000	>1000

Adapted from [Sheffield, 2013]

ULN: upper limit of normal.

CONFIDENTIAL209544 (RSV MAT-004)
Statistical Analysis Plan Amendment 3

Table below shows the toxicity grading for lab parameters that are not covered in [Sheffield, 2013] but calculated based on the references and guidance in [Abbassi-Ghanavati, 2009]

Laboratory Parameter	Grade 1	Grade 2	Grade 3
Hematocrit-2 nd trimester N 30.0-39.0 (%)	27-29.9 39.1-42.9	24-26.9 43-46.8	≤ 23.9 ≥ 46.9
Hematocrit-3 rd trimester N 28.0-40.0 (%)	25.2- 27.9 40.1-44	22.4-25.1 44.1-48	≤22.3 ≥48.1
Mean Corpuscular Volume MCV 2 nd trimester N 82-97 (μm ³)	73.8-81.9 97.1-106.7	65.6-73.7 106.8-116.4	≤65.5 ≥116.5
Mean Corpuscular Volume MCV 3 rd trimester N 81-99 (μm ³)	72.9-80.9 99.1-108.9	64.8-72.8 109-118.8	≤64.7 ≥118.9
RBC - 2 nd trimester N 2.81 – 4.49	2.6-2.8 4.5-4.9	2.3 – 2.5 5.0-5.3	≤2.2 ≥5.4
RBC - 3 rd trimester N 2.71-4.43	2.5-2.7 4.4-4.8	2.2 – 2.4 4.9-5.3	≤2.1 ≥5.4

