Safety analyses in **infant subjects** will include summaries by study group and gestational age at birth (> 37 weeks or ≤ 37 weeks) of neonatal AESIs, MAEs, SAEs, AEs leading to study withdrawal, and the occurrence of RSV-associated RTIs, LRTIs, severe LRTIs, very severe LRTIs and RSV-associated hospitalizations.

All safety analyses will be performed on the Solicited Safety or Exposed sets.

	Primary Safety Endpoints	Statistical Analysis Methods
Maternal subjects	Occurrence of Solicited administration site and systemic events that occur during a 7-day follow-up period after vaccination (i.e. the day of vaccination and 6 subsequent days).	
The number and percentage with exact 95% CI of maternal subjects reporting each Solicited administration site event (any grade, each grade,) and solicited systemic event (any, each grade) during the 7-day (days 1 to 7) follow-up period after vaccination will be tabulated by maximum intensity per subject for each study vaccine group.
 
For fever during the 7-day follow-up period after vaccination, the number and percentage of maternal subjects reporting any fever (i.e., temperature ≥ 38 °C) and fever by half degree (°C) cumulative increments, any Grade 3 fevers, will be reported. In addition, the prevalence of any and Grade 3 fever will be presented graphically over time after vaccination.
 
The number and percentage of maternal subjects with at least one administration site AE (solicited and unsolicited), with at least one systemic AE (solicited and unsolicited) and with any AE during the 7-day follow-up period after vaccination will be tabulated with exact 95% confidence interval (CI) by group. The same computations will be done for Grade 3 solicited and unsolicited AEs, for any AEs considered related to vaccination, for any Grade 3 AEs considered related to vaccination and for any AEs resulting in a medically attended visit (i.e., MAEs).

	Occurrence of any protocol-specified hematological or biochemical laboratory abnormality at baseline (up to 15 days before vaccination) and Day 8 (Visit 2)	The number and percentage of subjects with hematology and biochemistry results outside central laboratory normal ranges will be tabulated to show Day 8 versus baseline. The maximum grading as described in [Sheffield, 2013] and in the SPM from Screening up to Day 8 will also be tabulated.

CONFIDENTIAL209544 (RSV MAT-004)
Statistical Analysis Plan Amendment 3

	Primary Safety Endpoints	Statistical Analysis Methods

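### Laboratory grade bands in SAP section 9.1.4 overlap the normal range in two rows and leave gaps in others, with no rounding rule

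*SAP*

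**What the plan says.** Section 9.1.4 of SAP Amendment 3 prints grade bands by trimester: Table 11, adapted from a published pregnancy scale, and a supplementary table for haematocrit, MCV and RBC. The rows at issue are:

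- RBC, third trimester: "RBC - 3 rd trimester N 2.71-4.43", Grade 1 "2.5-2.7 4.4-4.8", Grade 2 "2.2 – 2.4 4.9-5.3", Grade 3 at or below 2.1 and at or above 5.4. The normal range has two decimals and the grades have one.
- RBC, second trimester: "RBC - 2 nd trimester N 2.81 – 4.49", Grade 1 2.6-2.8 and 4.5-4.9.
- Platelets, third trimester: normal "146-429 x 1000 L" (per litre), Grade 1 low 125-146.
- WBC, second trimester: normal "5.6-14.8 x 1000cell/mm" (cubed), Grade 1 low from below 5.5 down to 3.5.
- BUN: normal to 13.0 and Grade 1 14.0-19.0 (second trimester); normal to 11.0 and Grade 1 12.0-19.0 (third); Grade 2 from 20.0 in both.
- Creatinine: normal to 0.8 and Grade 1 from 0.9 (second trimester); normal to 0.9 and Grade 1 from 1.0 (third).

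Section 5.3.1 plans haematology and biochemistry summaries by grade and time point. Under the primary laboratory endpoint it first counts results outside the central laboratory's normal ranges, Day 8 against baseline, and then adds: "The maximum grading as described in [Sheffield, 2013] and in the SPM from Screening up to Day 8 will also be tabulated". Section 5.3.2.6 refers to section 9.1.4 for the grading details. The SAP gives no reporting precision, rounding rule or tie rule for these grades.

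**The concern.** A grading scale has to put every result in exactly one class. Where a value is both normal and Grade 1, its grade depends on the order in which the programmer tests the conditions. Where a value is in no band, it drops out of the by-grade table or is assigned by a rule invented at programming. Most of these faults lie at the edge of the normal range, where mildly abnormal values are most frequent. At stake is the accuracy of the Grade 1 counts, and of some Grade 2 and 3 counts for BUN and RBC, in tables reported under a primary safety endpoint.

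**Working it through.** There is no planned figure to reproduce. Each numeric row was coded with its printed open or closed limits, leaving out AST/ALT (contiguous multiples of ULN) and monocytes/basophils (percent outside normal). Values were scanned in steps of 1, 0.1 and 0.01 (platelets in steps of 1), listing those in no band or in more than one.

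**Overlaps (two, both normal with Grade 1)**

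- RBC, third trimester: normal ends at 4.43 and Grade 1 starts at 4.4, so 4.40-4.43 is in both.
- Platelets, third trimester: normal starts at 146 and Grade 1 low ends at 146, so 146 is in both.

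**Gaps**

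| Row | Values in no band | Precision needed |
|---|---|---|
| WBC, 2nd trimester | 5.5 | one decimal |
| BUN, 2nd trimester | 13.1-13.9, 19.1-19.9 | one decimal |
| BUN, 3rd trimester | 11.1-11.9, 19.1-19.9 | one decimal |
| RBC, 3rd trimester | 2.11-2.19, 2.41-2.49, 4.81-4.89, 5.31-5.39 | two decimals, as in its own normal range |
| RBC, 2nd trimester | 2.21-2.29, 2.51-2.59, 4.91-4.99, 5.31-5.39 | two decimals |
| Creatinine, next to normal | 0.81-0.89 (2nd), 0.91-0.99 (3rd) | two decimals |
| Creatinine, between grades | 1.21-1.29, 1.61-1.69 (both trimesters) | two decimals |

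Haemoglobin, haematocrit and MCV show similar slivers, also only at two decimals. The RBC gaps all lie between grades; there is none next to the RBC normal range.

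**Comparison with the other trimester**

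- Platelets, second trimester: normal from 155, Grade 1 to 154. Clean.
- WBC, third trimester: normal from 5.9, Grade 1 below 5.9. Clean.
- RBC upper edge, second trimester: normal to 4.49, Grade 1 from 4.5. Clean.

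These three faults are therefore slips in single cells. The BUN steps occur in both trimesters.

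**Size**

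Assume the printed normal limits are the 2.5th and 97.5th percentiles and results are continuous. With z = 1.96, the normal fit has mean (L+U)/2 and SD (U−L)/(2z). The lognormal fit uses the same formulae on ln L and ln U.

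- BUN, third trimester (3-11): mean 7.0, SD 8/3.92 = 2.04. P(11 to 12) is 1.8% (normal) or 1.2% (lognormal), against 2.5% above 11 by construction.
- Creatinine, third trimester (0.4-0.9): mean 0.65, SD 0.5/3.92 = 0.128. P(0.9 to 1.0) is 2.2% (normal) or 1.8% (lognormal).
- RBC, third trimester (2.71-4.43): mean 3.57, SD 1.72/3.92 = 0.439. P(4.40 to 4.43) is 0.43% (normal) or 0.33% (lognormal). If 4.40-4.43 is read as rounded two-decimal results, the limits become 4.395 and 4.435, giving 0.57% or 0.45%.

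**The case against.** Several points limit this, and most of them stand.

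- **No result carries two numbered grades.** A reader might infer that from the overlaps. The scan found no value in two numbered bands of one row at any resolution; the conflict is always normal against Grade 1.
- **The whole primary laboratory endpoint is not miscounted.** The count outside central laboratory normal ranges does not use these bands. A third-trimester BUN of 11.5 is still counted there if it lies outside the laboratory's range.
- **Precision is unknown.** If BUN is reported in whole mg/dL and creatinine to one decimal, their gaps vanish. At one decimal the only gaps next to normal are BUN and WBC 5.5. It is tempting to say that many mildly abnormal results go ungraded: under the fits above, the gaps hold 47-71% of high third-trimester BUN values and 73-88% of high creatinine values. Those are shares of an assumed 2.5% tail, and they need decimals that the SAP does not promise.
- **Unit conversion adds nothing.** The first SAP version showed conventional and SI units, but only for haematocrit, MCV and RBC, in a table since replaced. BUN and creatinine appear in mg/dL throughout.
- **Second-trimester rows have little reach.** Vaccination is at 28 0/7 to 33 6/7 weeks and baseline is at most 15 days earlier. If the third trimester starts at about 28 weeks (an assumption), those rows cover only some screening samples and no Day 8 sample. Both overlaps, however, are in third-trimester rows.
- **The SPM may hold a rule.** It is cited beside the grading and is not available here. Even so, the SAP prints its own bands, and those contradict themselves.

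One might also try to rebuild the RBC edges. The haematocrit and MCV bands match 90% and 80% of the lower limit and 110% and 120% of the upper. The same multiples for third-trimester RBC give 2.439, 2.168, 4.873 and 5.316. The SAP states no such rule. Ending Grade 2 at 5.32 while Grade 3 stays at 5.4 would still leave 5.33-5.39 without a grade.

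**Conclusion.** The point holds in a limited form. The bands in section 9.1.4 are neither mutually exclusive nor exhaustive. Four faults need no assumption beyond the precision of the printed limits: the third-trimester RBC overlap at 4.40-4.43, the third-trimester platelet overlap at 146, the missing second-trimester WBC value of 5.5, and the RBC gaps between grades at the two decimals of its own normal range. The BUN gaps need results with at least one decimal, and the creatinine gaps need two.

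The effect is misclassified or omitted results in the by-grade and maximum-grade tables. Under the central-95% assumption it is about 0.3-0.4% of third-trimester RBC samples and, where the precision allows, 1.2-1.8% for BUN and 1.8-2.2% for creatinine. These tables are descriptive, so no formal conclusion turns on them. The correction is nevertheless worth making, because the faults feed a primary safety endpoint and cost almost nothing to remove.

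**What to change.** Rewrite the bands in section 9.1.4 so that each row is contiguous and does not overlap its own printed normal range:

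- RBC, third trimester: start Grade 1 high above 4.43.
- Platelets, third trimester: end Grade 1 low below 146.
- WBC, second trimester: start Grade 1 low below 5.6.
- BUN: start Grade 1 above the upper normal limit (13.0 or 11.0) and run it up to the start of Grade 2.
- Creatinine and the other one-decimal rows: use the same contiguous convention.
- RBC, both trimesters: close the between-grade gaps on the low and high sides, with edges the sponsor reconciles to its source scale and the SPM.

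Add one sentence stating the unit and precision at which grading is applied, and whether values are rounded first. The cost is re-typed edges in one SAP section and a check of the grading program against them. Data collection and study procedures do not change.

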9.2. Statistical Method

Study specific statistical methods for immunogenicity analysis are described in section 5.2.2.

10. ANNEXES**10.1. Business rules for standard data derivations and statistical methods**

This section contains GSK Vaccines' standard rules for data display and derivation for clinical and epidemiological studies. These rules will be applied along with those detailed in section 9 (additional study-specific rules).

10.1.1. Attributing events to vaccine doses

The dose relative to an event is the most recent study dose given to a subject prior to the start of a given event.

If an event starts on the same day as a study dose, the relative dose will be derived from the additional information provided in the CRF using the contents of the flag indicating if the event occurred before or after vaccination. If 'after vaccination' is selected, the relative dose for the event will be the one administered on the start day of the event. If 'before vaccination' is selected, the relative dose for the event will be the dose prior to this one.

CONFIDENTIAL209544 (RSV MAT-004)
Statistical Analysis Plan Amendment 3**10.1.2. Handling of missing data****10.1.2.1. Dates**

When partially completed dates (i.e. with missing day or month) are used in calculations, the following standard rules will be applied:

- A missing day will be replaced by 15
- A missing day and month will be replaced by June 30th.

The following exceptions apply:

- Adverse event start dates with missing day:
 - If the event starts in the same month as at least one of the study doses, the contents of AE.AESTRTPT (the flag indicating if the event occurred before or after vaccination) will be used to complete the date. If ‘after vaccination’ is selected, the imputed start date will match the first (or only) study dose given during that month. If ‘before vaccination’ is selected, the imputed date will be one day before the first (or only) study dose given during that month.
- Adverse event start dates with missing day and month:
 - If the event starts in the same year as at least one of the study doses, the contents of AE.AESTRTPT (the flag indicating if the event occurred before or after vaccination) will be used to complete the date. If ‘after vaccination’ is selected, the imputed start date will match the first (or only) study dose given during that year. If ‘before vaccination’ is selected, the imputed date will be one day before the first (or only) study dose given during that year.

All other cases of incomplete AE or concomitant medication/vaccination start date will follow the standard rules above.

